## Protocol Body

### 1.0 Objectives

The objective of this study is to conduct a pilot 3-group randomized clinical trial involving three behavioral health interventions for smoking cessation among Latino smokers. Participants will be randomized to one of three interventions: A 1) Health Education (HE) control condition, a 2) Culturally Tailored Smoking Cessation (CTSC) condition or a 3) CTSC + Adherence Enhancement (AE) condition. All three conditions will include three behavioral intervention sessions with a counselor at baseline, 2 weeks and 6 weeks. Participants in all three groups will also receive 12 weeks of Nicotine Replacement Therapy in the form of nicotine patches. We will assess cessation at follow-up which will occur at 3 and 6 month follow up. The specific aims of this project are:

**Aim 1: Evaluate the feasibility, fidelity, and acceptability of the CTSC and CTSC+AE in Latino smokers.** Our evaluation of these domains will seek to identify elements of the intervention that are successful or in need of improvement for a planned larger trial. To evaluate these domains we will assess: 1) Recruitment and retention of participants 2) Intervention adherence 3) Program satisfaction 4) The extent to which the intervention was delivered as planned (derived from the Fidelity Checklist [Appendix Z], described in the measures section).

**Aim 2: To evaluate the preliminary efficacy of the CTSC and CTSC + AE, as compared to HE, on increasing biochemically verified 7-day point prevalence smoking abstinence rates at 3 and 6 month follow-up in Latino smokers.**

**Aim 3: To evaluate the efficacy of the CTSC+AE condition, as compared to the HE and CTSC groups, on increasing adherence to nicotine patch treatment (NRT adherence is defined as the proportion of days of NRT use over the number of patches made available).**

**Aim 4 (Exploratory): To examine potential mediators and moderators of the relationship between our primary outcomes (Aims 1-3) and our treatment groups.** For this exploratory aim we will examine several variables that may influence treatment outcomes including gender, age, alcohol use, health related fatalism, sense of control and acculturation.

### 2.0 Background

#### Tobacco Use and Smoking Cessation among Latinos

Latinos are the largest and fastest growing ethnic group in the United States (US). They constitute 16% of the population and by the year 2030, it is estimated that 20% of individuals residing in the US, will be Latino. Smoking has been identified as a significant and concerning public health problem among Latinos. In a recent national

survey of Latino health, an overall smoking prevalence rate of 16.9% was found with substantial disparities by gender and national origin. For example, smoking among Mexican American males (23.4%), Cuban males (31.3%) and females (21.9%), as well as Puerto Ricans males (35%) and females (32.6%) exceeds the smoking prevalence rate of non-Latino Whites (19.4%). Three of the four leading causes of death among Latinos are associated with smoking (cancer, heart disease, & stroke). Moreover, lung cancer is the foremost cause of cancer death for Latino men and the second leading cause for Latina women.

Latino smokers experience smoking cessation treatment disparities due to a general lack of health care access, under-utilization of existing services, and poor treatment outcomes. Various national surveys have determined that Latinos receive advice to quit smoking from their physician at lower rates than other ethnic/racial groups. In multiethnic/racial treatment studies, Latinos have been shown to have lower smoking cessation abstinence rates as compared to Whites. A relatively limited number of studies have tested smoking cessation interventions for Latino smokers. Of the existing studies, only six utilized an RCT design that included a control group and biochemical measures of smoking abstinence at follow-up. In Webb and colleagues (2010) meta-analysis that included five of these six studies, an odds ratio effect size (ESOR) of 1.54 (95% CI, 1.09-2.16) was calculated, indicating that the experimental treatments in the selected studies did have a significant effect on cessation rates. However, this effect was only found at the *end of treatment* and deteriorated by follow-up. Furthermore, the extent to which the treatments in these studies were actually culturally tailored to Latinos is questionable and raised as an area in need of further research.

It has been over 7 years since the US Department of Health and Human Services published its updated *Clinical Practice Guideline for Treating Tobacco Use and Dependence* (2008) which urged the advancement of research focusing on the development and testing of culturally adaptive smoking cessation for racial minority populations including Latinos. Since that time, there have only been three published RCTs of smoking cessation interventions for Latinos. Of the three, two of the studies (both from our own group) specifically sought to tailor an intervention to the unique cultural characteristics of Latinos. Considering the lack of research attention and the disparities in treatment among Latinos, smoking is likely to continue being a significant public health problem if further research is not conducted.

### **Adherence to Smoking Cessation Treatment among Latinos**

Studies have sought to explore the unique characteristics of Latino smokers that may influence the success of smoking cessation treatment. Levinson et al., demonstrated that Latinos are less likely to use pharmacotherapy treatments for smoking cessation than other ethnic/racial groups, even after controlling for factors such as health care access, income, physician advice to quit, health status and

smoking level. In a follow-up study Levinson et al., identified a number of potential barriers of Latinos with regard to pharmacotherapies including: concerns about side effects, fears of becoming dependent on medications, cultural inclinations towards quitting without chemical aid, a lack of knowledge about the effectiveness and use of medications, and misconceptions about the perceived risks of smoking.

Nicotine replacement therapy (NRT), the most commonly used and available smoking cessation pharmacotherapy aid, has been found to increase the likelihood of quitting by up to two-fold. However, studies have shown that when smokers are non-adherent to the full course of NRT there are lower follow-up abstinence rates. Latinos are particularly wary of utilizing any pharmacological aids for smoking cessation; therefore they are prone to NRT non-adherence. In our prior work, Latinos were found to have 56.6% adherence to a 12-week NRT patch regimen which is a considerably lower treatment dose than the recommended minimum practice guideline. The challenge of maintaining medication adherence among Latinos is not exclusive to NRT or smoking cessation. As compared to other ethnic/racial groups, Latinos have lower adherence rates to medications for chronic medical conditions such as diabetes, hypertension, HIV/AIDS, and psychiatric conditions.

Medication adherence poses a significant barrier to smoking cessation treatments for Latinos and the unique needs and concerns of Latino smokers who seek to quit requires the development of culturally tailored interventions. Previous studies seeking to develop Latino specific interventions have emphasized linguistic appropriateness, integrating values that are specific to Latinos, acculturation, and addressing specific gaps in knowledge or cultural traditions that may be barriers to treatment. These cultural domains have yet to be fully integrated with strategies for increasing adherence to smoking cessation treatment. The current study seeks to test a culturally tailored smoking cessation intervention + an adherence enhancement add-on intervention among Latinos smokers.

### 3.0 Background Drug Information

The efficacy of the nicotine patch has been extensively studied and each of the published meta-analyses concluded that the patch increased rates of smoking cessation. Nicotine patches will be purchased from an outside vendor and/or through the MDA Pharmacy. The patch used in this protocol is approved for over-the-counter sale and use. Due to the use of nicotine patches, taking part in this study can result in risks to an unborn or breastfeeding baby, and you should not become pregnant or breastfeed a baby while on this study.

## 4.0 Patient Eligibility

**Participants & Recruitment:** A total of 36 participants will be enrolled, 12 in each condition. We will recruit participants by posting flyers at locations in the greater Houston area that are known to be frequented by our target Latino population (ex: community centers, Hispanic food markets and grocery stores, salons, bus stations, clinics serving mainly Hispanics). We will also post ads in free Houston area Spanish language print newspapers (ex: La Subasta, Buena Suerte) as well as use radio ads heard throughout the greater Houston area. All ads and flyers will use the IRB approved advertisements. (See Appendix R).

### **Inclusion Criteria:**

- 1) Adults at least 18 years of age
- 2) Current smoker (>5 cigarettes per day for the past 3 months)
- 3) Able to speak and read English or Spanish
- 4) Agree to participate in the study and be available for 6 weeks of treatment and 6 months of follow-up
- 5) Willing to set a quit date within 2 weeks of enrollment date
- 6) Identify as being of Latino heritage, ethnicity, or ancestry

### **Exclusion Criteria:**

- 1) Individuals suffering from any unstable medical condition precluding the use of NRT (Identified using the Medical History Questionnaire given at baseline, See Appendix X)
- 2) Currently using smokeless tobacco, electronic nicotine delivery systems (ENDS), nicotine replacement therapy, or other smoking cessation treatment
- 3) Pregnant or nursing
- 4) Suffering from a severe psychiatric disorder (assessed using self-reported history of psychiatric diagnosis during the phone screening) that would interfere with participation
- 5) Diagnosis of substance dependence other than nicotine (screened using DSM IV TR criteria)
- 6) Individuals that do not have access to a working telephone

## 5.0 Pretreatment evaluation

**Recruitment:** Participants will be recruited through the recruitment strategies previously discussed in *Section 4.0: Patient Eligibility*. Potential participants will be screened over-the-phone by a research assistant using a checklist of the study inclusion and exclusion criteria (See Appendix C). Eligible and interested participants will be scheduled for a baseline visit, which will last approximately 2.5 hours at M.D. Anderson. Potential participants will be informed that the visit will entail a series of questionnaires and a one-on-one session with a counselor regarding their smoking and quitting. Participants will be informed that the entire visit will last approximately 2.5 hours and they will be compensated with a \$50 gift certificate. The day prior to their visit to M.D. Anderson, participants will receive a reminder call from a research assistant. The reminder call or voicemail message will not divulge any information regarding their participation in the study.

**Baseline Visit:** Study personnel will provide a detailed description of the study, answer questions, obtain written informed consent, and finalize eligibility. Participants will complete a series of questionnaires at baseline, and a trained research assistant will collect a sample of expired carbon monoxide using a Bedfont Micro+ Smokerlyzer®. Participants who are able to become pregnant will be required to take a routine hCG urine sample pregnancy test administered by the research assistant to rule out potential pregnancy.

**Measures** The assessment battery will be available in both English and Spanish languages. Based on our previous work with the proposed instruments, we estimate the battery of measures will take approximately 1.5 hours to complete at baseline and during the 3 and 6-month visits.

	Approximate time to complete (minutes)	Total for session
Baseline Visit		
Pregnancy Test (Females only)	5	
Demographics	20	
Medical History	5	
Tobacco History	10	
Fagerstrom (FTND)	5	
SRNT (Baseline)	15	
Alcohol Quantity & Frequency	5	
Sense of Control	5	
Religious Health Fatalism	5	
Bicultural Involvement (BIS)	10	
Smoking Status	2	
TLFB	5	92 minutes
Counseling Sessions (Visits)		

2 & 3)		
Adverse Events Monitoring (Completed with RA)	10	
Adherence-TLFB (Completed with RA)	10	
Smoking Status	2	
SRNT (Baseline or Post-Quit)	15	
Satisfaction Surveys	5	42 minutes
Follow-Up Visits (3 & 6 month)		
Demographics	20	
Medical History	5	
Tobacco History	10	
SRNT (Baseline or Post-Quit)	15	
Fagerstrom (FTND) – If non-abstinent	5	
Alcohol Quantity & Frequency	5	
Sense of Control	5	
Religious Health Fatalism	5	
Bicultural Involvement (BIS)	10	
Smoking Status	2	
Adherence-TLFB (Completed with RA)	10	92 minutes

*Demographics Questionnaire* (Appendix D) administered at baseline and follow-up will collect data on age, race, ethnicity, education, income, preferred language, and generations in the U.S. This questionnaire has been used extensively by our team.

*Medical History* (Appendix X) Participants will be asked to provide a detailed medical history including heart disease, asthma/lung disease, high blood pressure, diabetes, high cholesterol, thyroid problems, and kidney disease. Participants will also be asked to provide a detailed list of medications and their dosage that they take daily.

*Tobacco History* (Appendix E) collects information regarding onset of regular smoking, previous quit attempts, abstinence history, smoking rate, other household smokers, proportion of friends/family who smoke, and other tobacco use. This questionnaire has been used extensively by our team.

The *Fagerstrom Test for Nicotine Dependence* (FTND) (Appendix F) is a widely used measure of nicotine dependence. The *Heaviness of Use Index* is composed from a portion of the items on the larger measure. Six questions from the Fagerstrom questionnaire will be used in this protocol.

*Society for Research on Nicotine and Tobacco (SRNT) Abstinence Status Questionnaire* (pre- and post-versions) (Appendix G) surveys tobacco use by the

participant and persons within the participant's household and social surroundings.

The *Alcohol Quantity and Frequency Measure* (Appendix H) assesses quantity and frequency of alcohol consumption and is adapted from Cahalan (1973).

*Sense of Control* (Appendix I) balances claiming versus denying control statements for good and for bad events, cancels the agreement bias that commonly exists when using Likert-scaled items, and improves the validity of the sense of control measure.

*Religious Health Fatalism Questionnaire (RHFQ)* (Appendix J) Religious Health Fatalism is defined as "the belief that health outcomes are inevitable and/or determined by God", and assess the association between Religious Health Fatalism and health behaviors among individuals.

*Bicultural Involvement Scale (BIS)* (Appendix K) is a 24-item self-report measure used to assess cultural orientation. The measure generates scores for individuals' independent association with each of the two cultures, their degree of biculturalism, and a rating of their total cultural involvement. Originally developed for use with Hispanic and American individuals, the measure has also been modified for use with individuals from other cultures, including Asia and Australia. Adapted from the acculturation scale, the bicultural involvement questionnaire was developed by José Szapocznik, William M. Kurtines, and Tatjana Fernandez in 1980 as a multidimensional tool for measuring cultural orientation. Unlike the majority of acculturation measures that preceded it, the BIQ does not assume that involvement in one culture necessitates exclusion of association with another.

*Smoking Status* will be assessed at each study visit. Self-reported abstinence will be verified using expired carbon monoxide testing using a Bedfont Micro+ Smokerlyzer® at the 2 and 6-week sessions and 3 and 6-month follow-up assessments.

**Randomization:** After the Baseline Visit, participants will be randomly assigned to CTSC, HE, or CTSC+AE using a standard urn randomization technique (1:1:1) stratified by gender.

## 6.0 Treatment Plan

The proposed pilot study is a 3-group RCT of 36 Latino smokers with all participants receiving 12-weeks of nicotine patch treatment and self-help materials. Participants randomized to our experimental conditions (CTSC and CTSC+AE) will receive 3 individual counseling sessions incorporating Latino cultural tailoring (described below). The CTSC+AE group will receive counseling session content that specific emphasizes techniques and strategies for improving NRT adherence as well as discussions relating to the emerging themes and issues garnered from the qualitative portion of this study (Project Impact 2, Protocol #2015-0585) The HE control condition will also receive 3 sessions with a counselor focused on general health education and smoking.

Treatment manuals for HE, CTSC, and CTSC+AE will be used to ensure standardization of treatment delivery as well as to provide a basis for evaluating therapist competence and adherence. All participants will attend 2 follow-up assessment visits occurring at 3 and 6 months post-treatment. Randomization: Participants will be randomized into one of three treatment conditions in a 1:1:1 distribution (CTSC, CTSC+AE or HE). Compensation: Participants will be compensated for all study visits with gift certificates. The compensation schedule will be as follows: Baseline assessment-\$50; Session 2-\$40; Session 3-\$60; 3-month follow-up \$75; and \$100 for the 6 month follow-up. Participants that drive to the medical center will be reimbursed for parking; those using public transportation will be given public transit passes.

Treatment Components Included in Both Conditions: Participants in all three arms of the study will receive Nicotine Replacement Therapy (NRT), which is the most commonly used and available smoking cessation pharmacotherapy. The use of NRT during a quit attempt is associated with a 50-70% increase in cessation rates. Thus, NRT is a well-established and empirically supported first-line treatment for individuals seeking pharmacotherapy for smoking cessation. Furthermore, when NRT is coupled with a behavioral intervention such as counseling, cessation rates substantially increase by up to 16%. Therefore, the combination of a behavioral intervention with NRT is widely considered an optimum level of treatment. All participants (CTSC, CTSC+AE and HE conditions) will receive 12 weeks of NRT patch treatment - Nicoderm CQ (GlaxoSmithKline, Philadelphia, PA). Participants will be advised to use the patch according to the standard tapering schedule: 4 weeks of 21 mg, 4 weeks of 14mg, and 4 weeks of 7mg patches. Patch dispensation will occur at study visits. Participants receive only the number of patches necessary to last until the next study visit plus several extra patches should a patch fall off, become torn, etc., or should the visit be delayed. Based on our previous research, providing subjects with only enough patches to last until the subsequent visit improves compliance. A reduction in dosage or cessation of the patch regimen will be implemented for any participant who shows signs of being on too high of a dose. This is typically necessary for very few participants because blood nicotine levels are usually much lower on the patch than while smoking.

 Self-Help Materials: Self-help materials will consist of the consumer products

developed for the *Treating Tobacco Use and Dependence Clinical Practice Guideline*.

During the first session and irrespective of treatment condition, the interventionist will work with the participant to set a quit date within two weeks (participant's willingness to set a quit date within 2 weeks is an inclusion criteria for the study). The process of setting a quit date will follow the *Treating Tobacco Use and Dependence Clinical Practice Guidelines* and the interventionist will engage in a discussion about the ideal date and the consideration of various scheduling factors (e.g., a weekend date versus weekday).

Health Education Control Condition: We will use a Health Education intervention as our control condition. The duration of the three health education sessions and their timing (after the assessment at baseline, 2 and 6 weeks) will be identical to the experimental conditions. The 3 sessions will cover: 1) smoking and health, 2) nutrition/exercise (Appendices U/W) and 3) sleep hygiene (Appendix V). These sessions will primarily be didactic and consist of health education, followed by discussions and questions about the material and how it might relate to smoking. Our investigative team has conducted such health education interventions in previous studies. We will replicate this work and develop handouts and illustrations for the HE sessions. See Appendix S for HE manual.

Culturally Tailored Smoking Cessation Treatment: The CTSC intervention has been developed based on Kreuter and colleagues' (2003) *Five Strategies Model of Cultural Tailoring* of health interventions. The five strategies are: 1) Peripheral Strategies—design materials and programs so as to make them appear culturally relevant; For example, the use of brochures depicting images of Latino smokers instead of non-culturally specific imagery. 2) Evidential Strategies – the presentation of evidence to participants that is directly related to their respective group. For example, rather than simply stating that smoking causes cancer, a counselor may say “16.9% of Latinos smoke and lung cancer is the leading cause of cancer death among Latino men.” 3) Linguistic – assuring that materials and programs are in the language of your select group. This is self-explanatory. 4) Constituent-Involving Strategies – approaches that aim to directly draw upon the experience of members of the targeted group. For example, hiring counselors that are Latino or have a history of working in the Latino community. Lastly, 5) Sociocultural strategies attempt to integrate health issues within the broader socio and cultural context. For example, integrating elements of the target group’s cultural values, beliefs, and behaviors during discussions. (See Appendix T for CTSC manual)

All components of the CTSC will be linguistically appropriate (either in English or Spanish) and delivered by counselors who are Latino and have clinical experience in smoking cessation as well as in working with Latinos in Houston. Other elements of our cultural tailoring will replicate our previous work and the first session will be initiated with informal conversations about family and cultural background in order to enhance rapport and emphasize the Latino values of *respeto*, *personalismo*, and *familismo*. The

counselor will provide participants with an empirically validated smoking cessation self-help booklet for Latinos – “*No Lo Deje Para Mañana, Deje De Fumar Hoy – Una Guía Para Dejar De Fumar*” (NIH Publication No. 02-3001) (Appendix O). This manual (“Guía”) consists of 36 full color pages of simple text and photographs that includes information about smoking, quitting, relapse prevention strategies, and personal testimonials. The content of the Guía was specifically developed to be culturally sensitive to Latinos and was found to be acceptable during the focus group phase of Project Aurora. The Guía has also been shown to improve verified quit rates among Latinos at one-year follow-up. In addition, the importance of social support during a quit attempt will be discussed and the counselor will work closely with the participant to identify ways to enhance social support particularly through family, during the quit attempt. Lastly, the counselor will integrate pan-Latino values identified by Marin & Marin (1991), into all aspects of the intervention. For example *machismo* (association between masculine ideals and the use of pharmacotherapy, smoking and *familismo* (responsibility to family, including setting examples for children), and the de-emphasis of *fuerza de voluntad* (willpower) as the primary means for achieving cessation, as well as the de-emphasis of *fatalismo* (fatalistic outlook) of health and wellness have all been recognized in the literature and will be integrated into session content.

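### Nothing limits enrolment to one smoker per household, so housemates can be randomised to different arms; any bias is probably small, but one screening question would prevent it

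*Combined protocol and SAP*

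**What the plan says.** **Who can enrol.** Section 4.0 lists six inclusion and six exclusion criteria, repeated in Section 12.0. None mentions a household, spouse or relative. The nearest exclusion concerns the volunteer's own tobacco products and treatment, "Currently using smokeless tobacco, electronic nicotine delivery systems (ENDS), nicotine replacement therapy, or other smoking cessation treatment", and the list ends with "Individuals that do not have access to a working telephone". Section 5.0 describes the phone screen as a checklist of these same criteria. The checklist itself (Appendix C) was not available.

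**How people are found.** Section 4.0 recruits by "posting flyers at locations in the greater Houston area that are known to be frequented by our target Latino population", with examples such as "community centers, Hispanic food markets and grocery stores, salons, bus stations, clinics serving mainly Hispanics", plus newspaper and radio advertising.

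**How they are allocated.** "A total of 36 participants will be enrolled, 12 in each condition", allocated "using a standard urn randomization technique (1:1:1) stratified by gender" (Section 5.0). No household term appears.

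**What differs between arms.** Section 6.0 has the CTSC counselor work with the participant to "identify ways to enhance social support particularly through family, during the quit attempt". It also gives CTSC participants the Guía, a self-help booklet said to have improved verified quit rates at one year. CTSC+AE contains all of CTSC and adds adherence strategies. Neither the booklet nor the family-support work appears in the HE description. All arms take home the same patches, with several spares.

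**What is recorded.** The Tobacco History covers "other household smokers, proportion of friends/family who smoke", and the SRNT questionnaire also asks about tobacco use in the household. Neither is used for enrolment, allocation or analysis.

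**What is analysed.** Section 11.0 plans Fisher's exact and Kruskal-Wallis tests, with the emphasis on the size of between-group differences. Its design considerations cover baseline imbalance and unequal session time, but not contamination or shared households.

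**The concern.** Two smokers in one home can answer the same flyer, and each is then allocated separately. If one goes to HE and the other to CTSC or CTSC+AE, the HE participant may read the booklet or hear the adherence advice second-hand. On the protocol's own account the booklet is an active ingredient. Adherence (Section 7.0) is days of use divided by patches made available, so patches passed between housemates would also distort the measure for both.

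What is at stake is the observed difference between arms. Section 11.0 names its magnitude as the focus, and the results are meant to inform a larger trial. Because nobody records which participants live together, any leakage could not be detected or corrected afterwards.

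**Working it through.** The plan gives no figure for household co-enrolment or contamination, so there is none to reproduce. The steps below show what the gap could do.

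**Inputs from the documents**
- 36 participants, 12 per arm (Section 4.0).
- Expected adherence of 56% in HE and 80% in CTSC+AE, SD 36 points, 20% attrition (Section 11.0). The planned contrast is 80 − 56 = 24 points, with 12 × 0.8 = 9.6 evaluable per arm.

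**Inputs assumed**
- Number of co-enrolled pairs, h: 2, 4 or 6.
- Share of the adherence effect that reaches an HE housemate, c: 0.5 to 1.

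**Step 1: chance that a pair is split**
- Independent 1:1:1 allocation: 2/3 = 0.67.
- Exactly 12/12/12: the second person has 35 places left, 24 of them in other arms, so 24/35 = 0.69.
- Gender strata change this little. A same-gender pair in a stratum of 18 (assumed) filled 6/6/6 gives 12/17 = 0.71.

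**Step 2: number of split pairs**
- Expected number = h × 24/35, which is 1.4, 2.7 and 4.1 for h = 2, 4 and 6.
- With two pairs, the chance of at least one split is 1 − (1/3)² = 0.89, or 1 − (11/35)² = 0.90.
- These figures are conditional on pairs enrolling, and they measure the chance of a split, not the amount of bias.

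**Step 3: dilution of the 24-point contrast**
- Share of HE participants with a housemate in CTSC+AE: f = (2h/36) × (12/35).
- Diluted contrast = 24 × (1 − f × c).
- Power = Φ(d / (36 × √(2/9.6)) − 1.96), where d is the contrast and 36 × √(2/9.6) = 16.43.

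| Pairs h | f | Contrast, c = 0.5 | Contrast, c = 1 | Power |
|---|---|---|---|---|
| 0 | 0 | 24.0 | 24.0 | 31% |
| 2 | 0.038 | 23.5 | 23.1 | 30–29% |
| 4 | 0.076 | 23.1 | 22.2 | 29–27% |
| 6 | 0.114 | 22.6 | 21.3 | 28–25% |

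**Step 4: correlated outcomes within a pair**
- With 12 per arm and independent outcomes, the variance of a difference between two arm means is 2σ²/12 = 24σ²/144.
- Let ρ be the correlation within a pair. A pair split between those two arms subtracts 2ρσ²/144. A pair inside one of them adds 2ρσ²/144.
- Either way the relative change is ρ/12 per pair. With positive ρ, a split pair makes the test conservative and a same-arm pair makes it anti-conservative.

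**The case against.** The strongest objection is that nothing shows the problem will occur. No co-enrolment rate is given, and at zero pairs there is no bias. That stands. So does the point on size: with two pairs the contrast moves by less than 1 point against an SD of 36, in a pilot that says it is not powered for formal testing.

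Other objections rule out stronger readings that a reader might infer:

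- **That CTSC is delivered through the family.** Section 6.0 specifies individual sessions. Family support is discussed with the participant and is one component among several. The adherence techniques are discussed in session, and no take-home material for them is described. The documented item that can travel is the booklet.
- **That household smoking must be common because the questionnaire asks about it.** It is a general instrument the team uses widely, and a question says nothing about frequency.
- **That patch sharing creates or removes a treatment difference.** Every arm receives the same patches, so co-enrolled housemates have little reason to share. Sharing would affect measurement only. Supply is limited to the next visit plus spares, and the patch count is one of three adherence methods.
- **That the p-values are invalid because participants are not independent.** Step 4 shows that the direction depends on the pair, and about two-thirds of pairs would be split.

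What the objections leave untouched is that no safeguard is described, that the booklet is confined to the CTSC arms and is called effective, and that the gap cannot be repaired after enrolment. Being a pilot is not a full answer, because the between-group magnitude is what the pilot is meant to supply.

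**Conclusion.** The gap is real and minor. Several smokers from one household can enrol, and a co-enrolled pair would be separated about two-thirds of the time (2/3 to 24/35). If that happened, the between-group differences would be pulled modestly toward zero: from 24 points to about 23.5–23.1 with two pairs, and 22.6–21.3 with six, a relative loss of 2% to 11%. This rests on assumed numbers of pairs and an assumed transfer of 50 to 100%. It also assumes that the adherence gain belongs to CTSC+AE alone.

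The documents do not support calling the tests anti-conservative overall; that holds only for same-arm pairs. Nor do they support extending the point to people who took part in the related qualitative study (Protocol #2015-0585). That protocol was not available, and nothing here shows how earlier participation would bias this comparison.

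**What to change.** Add one exclusion criterion to Section 4.0 and to its repeat in Section 12.0: *another member of the household is already enrolled in this study*. Ask it at the phone screen. No stated sample size or analysis changes.

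The cost is one eligibility line, one screening question and a few otherwise eligible people turned away, which could slow recruitment slightly. The rule does not reach relatives living elsewhere, or patches given to household smokers who are not enrolled.

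Two alternatives turn nobody away. Allocating a household to a single arm removes cross-arm leakage, but it makes every pair a same-arm pair, so the analysis would have to allow for clustering. Recording household membership alone would show whether pairs enrolled, but would not prevent leakage. For 36 participants the exclusion is the simplest.
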